8.5 Exploratory Categorical Analysis of PD

In addition to analyzing PD as continuous variable, it is often useful to analyze PD categorically. The following may also be summarized descriptively:

- Percent of subjects in each group with a mean PD change from baseline <-4mm, <-3mm, <-2mm, <-1mm, -1mm to 1mm, >1mm, >2mm, >3mm, >4mm at 90, 180 and 270 days
- Percent of subjects with pockets decreasing by 2mm or more that at baseline were < 5mm at 90, 180, and 270 days.
- Percent of tooth sites in each group with a mean PD change from baseline <-4mm, <-3mm, <-2mm, <-1mm, -1mm to 1mm, >1mm, >2mm, >3mm, >4mm at 90, 180 and 270 days
- Percent of subjects in each group with a mean PD <5mm, <6mm and < 7mm at 90, 180 and 270 days
- Percent of subjects in each group with all PD <5mm, <6mm and < 7mm at 90, 180 and 270 days
- Percent of subjects with 75% of pockets < 5mm that at baseline were < 5mm at 90, 180, and 270 days.
- Percent of tooth sites in each group with a mean PD <5mm, <6mm and < 7mm at 90, 180 and 270 days
- Percent of subjects in each group with PD <5mm at day 90 by baseline PD

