
Duration of Treatment:
 
Group 1: ST266 dosed daily on Days 1-5, 8-12, 22, and 30, and then monthly for 7 months (Days 60, 90, 120, 150, 180, 210, and 240).
 
Group 2: ST266 dosed 2x/week (with at least one day between treatments) for the first 3 months and monthly for 5 months thereafter (Days 120, 150, 180, 210, and 240).
 
Group 3: Placebo dosed at the same frequency as Group 1.

Placebo, Dosage, and Mode of Administration: Sterile saline (0.9% NaCl) will be applied in the same manner and in the same volume as the investigational product, ST266.

Criteria for Evaluation:
 
Efficacy:
 
The primary efficacy endpoint of this study is the change from baseline in the PD for each patient at 9 months (Day 270) for those pockets ≥ 6mm at baseline.
 
Secondary efficacy endpoints of this study are:
 
(1) Change from baseline in CAL at 9 months and (2) change from baseline in BOP at 9 months for those pockets ≥ 6mm at baseline.
 
Exploratory endpoints of this study are:
 
(1) Pro-inflammatory mediators, enzymes and bone markers will be measured in gingival crevicular fluid (GCF) and serum at the baseline, Days 15, 90, 180, and 270;
 
(2) Microbial analysis of periodontal flora will be performed at baseline and at Days 15, 90, 180, and 270; and
 
(3) Change from baseline in radiographic bone levels (RBL) at Days 90 and 270. PD, CAL, BOP, and FMPI will also be summarized at Days 90, 180 and 270.
 
(4) Smoker/treatment interaction will be summarized for PD and CAL at Days 90, 180, and 270.
 
(5) Percent of patients with all pockets < 5mm will be summarized at Days 90, 180 and 270.
 
(6) Percent of patients with pockets decreasing by 2mm or more that at baseline were ≥ 5mm will be summarized at Days 90, 180 and 270.
 
(7) Percent of patients with 75% of pockets < 5mm that at baseline were ≥ 5mm will be summarized at Days 90, 180 and 270.
 
Safety: The safety endpoints are frequency and pattern of adverse events (AEs) and serious adverse events (SAEs).

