2.1 Study Objectives

The primary objective is to estimate the efficacy of ST266 to reduce pocket depth (PD) as an adjunctive to scaling and root planing (SRP).

The secondary objectives of this study are to determine: (1) safety as established by assessment of AEs and SAEs, and (2) changes in the following clinical parameters:

- Clinical attachment level (CAL)
- Bleeding on probing (BOP)

Additional exploratory objectives are to compare the effects of the treatments and dosing schedules in the following:

- Proinflammatory mediators, enzymes, and bone markers in gingival crevicular fluid (GCF) and serum
- Periodontal flora as determined from microbial analyses
- Radiographic bone level (RBL)
- Full-mouth plaque index (FMPI)
- Percent of patients with all pockets < 5mm
- Percent of patients with pockets decreasing by 2mm or more that at baseline were ≥ 5 mm
- Percent of patients with 75% of pockets < 5mm that at baseline were ≥ 5 mm

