Exploratory Endpoints: Pro-inflammatory mediators, enzymes, and bone markers will be measured in GCF and serum at baseline and Days 15, 90, 180, and 270. Microbial analysis of periodontal flora will be performed at baseline and at Days 15, 90, 180, and 270. Change from baseline in RBL will be measured at Days 90 and 270. PD, CAL, BOP, will also be analyzed at Days 180 and 270. FMPI will also be analyzed at Days 90, 180 and 270. Percent of patients with all pockets $<$ 5mm, percent of patients with pockets decreasing by 2mm or more that at baseline were \geq 5mm, and percent of patients with 75% of pockets $<$ 5mm that at baseline were \geq 5mm will be shown at Days 90, 180 and 270.

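### SAP 8.5 selects pockets < 5 mm at baseline for two exploratory responder summaries that SAP 2, 2.1 and 2.2 define on pockets ≥ 5 mm

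*SAP*

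**What the plan says.** Three sections of the SAP define the two responder summaries on pockets that were deep at baseline.

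- SAP 2 (Protocol Summary), exploratory endpoint 6: "Percent of patients with pockets decreasing by 2mm or more that at baseline were ≥ 5mm". Exploratory endpoint 7: "Percent of patients with 75% of pockets < 5mm that at baseline were ≥ 5mm will be summarized at Days 90, 180 and 270".
- SAP 2.1 (Study Objectives): "Percent of patients with pockets decreasing by 2mm or more that at baseline were ≥ 5 mm" and "Percent of patients with 75% of pockets < 5mm that at baseline were ≥ 5 mm".
- SAP 2.2 (Overall Study Design and Plan), exploratory endpoints: "percent of patients with pockets decreasing by 2mm or more that at baseline were", followed by the same threshold of 5 mm or more. The 75% summary is given there with that threshold too, and both are to be shown at Days 90, 180 and 270.

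SAP 8.5 (Exploratory Categorical Analysis of PD) introduces its list with "The following may also be summarized descriptively". Two of its bullets read "Percent of subjects with pockets decreasing by 2mm or more that at baseline were < 5mm at 90, 180, and 270 days" and "Percent of subjects with 75% of pockets < 5mm that at baseline were < 5mm at 90, 180, and 270 days".

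The protocol's own list of exploratory endpoints contains neither summary, so the SAP is the only source for their definition.

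**The concern.** The bullets in 8.5 match the endpoints in SAP 2 almost word for word and name the same visits, but the baseline inequality points the other way. SAP 8.3.4 (Exploratory Efficacy Analyses) does not mention either summary. Section 8.5 is therefore the only part of the analysis chapters that lists them, and table specifications may well be written from it.

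Tables built on the 8.5 wording would not describe the endpoints stated in SAP 2. A very high percentage in every arm on the 75% summary could be misread as a high response rate, or as evidence that the arms do not differ, when it mostly reflects which pockets were selected.

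**Working it through.** No power, sample size or alpha figure bears on this point. The check compares the definitions and then asks which recorded pocket depths each one admits.

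**Definitions side by side**

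| Summary | SAP 2 | SAP 2.1 | SAP 2.2 | SAP 8.5 |
|---|---|---|---|---|
| Decrease of 2 mm or more | baseline ≥ 5 mm | baseline ≥ 5 mm | baseline ≥ 5 mm | baseline < 5 mm |
| 75% of pockets < 5 mm | baseline ≥ 5 mm | baseline ≥ 5 mm | baseline ≥ 5 mm | baseline < 5 mm |
| Visits | Days 90, 180, 270 | not stated | Days 90, 180, 270 | Days 90, 180, 270 |

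**Measurement scale.** Protocol 11.1 records pocket depth in whole millimetres, rounding down. A baseline below 5 mm is therefore a recorded 4 mm or less, and the complement is a recorded 5 mm or more.

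**75% summary.**
- With baseline < 5 mm, every eligible pocket already satisfies the < 5 mm target. At baseline, 100% of eligible pockets meet it, and 100% exceeds 75%, so every subject with such pockets starts as a responder. Taking 75% to mean at least 75%, a subject becomes a non-responder only if more than 100% − 75% = 25% of these pockets deepen to 5 mm or more.
- With baseline ≥ 5 mm, no eligible pocket meets the target at baseline, so every subject starts as a non-responder and must improve to count.

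**2 mm summary.** The depth a pocket must reach is baseline minus 2 mm, or less.

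| Recorded baseline | Must reach | Admitted by 8.5 | Admitted by 2, 2.1, 2.2 |
|---|---|---|---|
| 1 mm | 1 − 2 = −1 mm: impossible | yes | no |
| 2 mm | 2 − 2 = 0 mm | yes | no |
| 3 mm | 3 − 2 = 1 mm or less | yes | no |
| 4 mm | 4 − 2 = 2 mm or less | yes | no |
| 5 mm | 5 − 2 = 3 mm or less | no | yes |
| 6 mm | 6 − 2 = 4 mm or less | no | yes |

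**Who is left out.** Inclusion criterion 6 requires at least 6 teeth with pocket depth ≥ 6 mm, and the primary endpoint uses sites ≥ 6 mm. All of those pockets fail the 8.5 filter and pass the filter in SAP 2, 2.1 and 2.2. Under the ≥ 5 mm definition, every subject who meets criterion 6 contributes pockets to both summaries.

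**Count affected.** Two summaries at three visits: 2 × 3 = 6 tabulated results per arm.

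**The case against.** The best defence is that 8.5 need not override anything. SAP 2 and 2.2 commit to the ≥ 5 mm versions, while 8.5 only permits its list. Read literally, the ≥ 5 mm summaries are required and the < 5 mm ones are optional extras. No text gives 8.5 precedence over three consistent statements in the same document, so it is not established that the tables will be run on shallow pockets. That much stands.

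It does not remove the conflict. Nothing in the SAP announces a separate shallow-pocket summary, and the near-identical wording points to a slip. If extras were intended, the two ≥ 5 mm endpoints would have no entry in the analysis chapters, and 8.5 would still need an addition.

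A reader might also infer that neither summary, as written in 8.5, could show any treatment effect. The documents do not support that. Pockets recorded at 3 or 4 mm can fall by 2 mm; they have little room rather than none. Shallow pockets can deepen by Day 90, 180 or 270, so the 75% summary could fall below 100% and could differ between arms. What is lost is the intended meaning, response in diseased pockets.

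Finally, little information about deep pockets would disappear altogether. The same section also lists subjects with all pockets below 5, 6 and 7 mm, mean depth below those limits, and categories of change. That limits the consequence but does not settle which definition applies.

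**Conclusion.** The contradiction is real: three sections say ≥ 5 mm, 8.5 says < 5 mm in two bullets, and nothing reconciles them. Followed as written, 8.5 would produce two summaries that do not measure the stated endpoints.

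The scope is narrow. Both summaries are exploratory and descriptive, 8.5 attaches no test or p-value to them, and they are not in the protocol. A reader might infer that the trial's efficacy conclusions are at risk; they are not, because the primary analysis, the secondary analyses of CAL and BOP, the multiplicity rule and the sample size do not use these bullets.

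The conclusion rests on two assumptions: that the three agreeing sections express the intent, and that table specifications may be drawn from 8.5. The first is strongly supported by the text. The second is plausible but not stated.

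**What to change.** In both 8.5 bullets, change the baseline condition from < 5 mm to ≥ 5 mm, to match SAP 2, 2.1 and 2.2. The < 5 mm target in the 75% summary stays as it is. If shallow-pocket summaries are also wanted, list them separately and label them as such.

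In the same edit, state for the 2 mm summary how many of a subject's eligible pockets must decrease (any, all or a stated share), because no section says so.

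The correction costs two symbols and, for the second item, one sentence. It needs no new data and no protocol change. It is best made before the Day 270 unblinding, so that the choice of definition cannot be questioned as made with results in view.

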8.6 Pooled comparisons

In addition to the above analyses that compare results between each active treatment group (N=50/group) and the placebo group (N=50), “pooled” analyses will be performed that combine the data from both active treatment groups (N=100) for comparison to the placebo group (N=50). Point estimates and 95% confidence intervals will be presented for change from baseline at each assessment time point. The p-values will not be presented for these analyses.

9. SAFETY EVALUATION

9.1 Overview of Safety Analysis Methods

Safety analyses will be presented descriptively on the safety population. No statistical testing will be performed.

9.2 Extent of Exposure

Treatment compliance will be presented at each visit and overall by group using both continuous summary statistics and the following frequency cut-offs: <50%, 50 - 80%, 80 - 90%, >90%.

Treatment compliance will be calculated as:

$$\left[\frac{\text{\# doses completed within X days (within 3 days in the first 60 days; within 5 days at Day 90; within 7 days at Day 180) from original scheduled dose date}}{\text{\# planned doses}} \right] * 100$$

Duration of therapy will be summarized by treatment group using continuous summary statistics. Duration of therapy in months will be calculated as:

$$\frac{\text{\text{last dose date}} - \text{\text{first dose date}} + 1}{30.4375}$$

Number of doses received will be summarized by treatment group using continuous summary statistics.

Information regarding the extent of exposure will also be presented in a listing presenting subject, dosing schedule/treatment group, planned dosing day, whether the subject was dose within X days (within 3 days in the first 60 days; within 5 days at Day 90; within 7 days at Day 180), actual dosing day, treatment compliance, duration of therapy, and number of doses received.

9.3 Adverse Events

The most recently available MedDRA dictionary version will be used for the classification of adverse events.

On-study AEs are those with a start date on or after the first treatment dose date and prior to the last treatment dose date + 30 Days.

On-study adverse events will be summarized overall by treatment group and by worst severity. Drug-related adverse events will also be tabulated.

All adverse events will be presented in a listing which includes first treatment dose date, onset and resolution date/day (or whether it is ongoing), system organ class and preferred term, investigator term, whether the event is serious, whether the adverse event involves

hematuria or proteinuria, severity grade, relationship to study drug, action taken, sequelae, and outcome.

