**Table 3: Study Design and Schedule of Assessments**

Evaluation	Treatment and Follow-up Period									
	Visit 1 Screening	Visit 2 Baseline (≤30 days from screening)	Visit 3/3b SRP (≤10 days from baseline)	Visit 4 Day 1 a (≤3 days from SRP)	Visit 5 Day 15 (±1 day)	Visit 6 Day 30 (±3 days)	Visit 7 Day 60 (±3 days)	Visit 8 Day 90 (±5 days)	Visit 9 Day 180 (±7 days)	Visit 10/EOS Day 270 (±7 days)
Informed Consent	X									
Pregnancy Test (female subjects)	X									X
Demographics	X									
Inclusion/Exclusion	X	X								
Dental History	X									
Medical History	X									
Vital Signs	X	X	X	X	X	X	X	X	X	X
Height and Weight	X b									X
Medical/Dental History Update g		X	X	X	X	X	X	X	X	X
Oral Exam	X	X	X	X	X	X	X	X	X	X
Randomization SRP d			X c X							
Full Mouth Plaque Index (FMPI)		X			X	X	X	X	X	X
Clinical Measurements (PD, CAL, BOP)	X				X	X	X	X	X	X
GCF Sampling		X			X			X e	X e	X
Serum Sampling		X			X			X	X	X
Microbial Sampling		X			X			X	X	X
Radiographs		X						X		X
General Labs	X f							X		X
Administration of Test Article				In-office treatments as scheduled in Figure 1						
Oral Hygiene Instruction g	X	X	X	X	X	X	X	X	X	X
Adverse Events g	X	X	X	X	X	X	X	X	X	X
Concomitant Medication g	X	X	X	X	X	X	X	X	X	X

BOP=bleeding on probing; CAL=clinical attachment level; EOS=end of study; FMPI=full-mouth plaque index; GCF=gingival crevicular fluid; HbA1c=glycated hemoglobin;

IWRS=interactive web response system; PD=pocket depth; SRP=scaling and root planing.

a The first in-office treatment may be performed on the same day as the last SRP visit. The last SRP may occur on Visit 3/3b, or as an Unscheduled Visit. The Unscheduled Visit may be combined with Visit 4. Product administration must occur within 3 days of the last SRP visit.

b Height is measured only at screening.

c Randomization occurs by IWRS after SRP has been completed.

d SRP may be initiated on the same day as the Baseline visit and may require more than one visit. Subjects with moderate to heavy deposits will typically have no more than two quadrants treated in a single SRP visit. Local anesthesia must be used for SRP.

[figure not shown]
e Sample is collected before treatment is applied.

f HbA1c is measured at screening only.

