#### **12.2.2. Adverse Event (AE)**

An AE is defined as any untoward or unfavorable medical occurrence associated with the subject's participation in the research, whether or not considered related to the subject's participation in the research. Any medical condition that is present at the time that the subject is screened will be considered as medical history and not recorded as an AE; however, if the condition worsens at any time during the study, it will be recorded and reported as an AE.

All AEs that occur after any subject signed consent, before treatment, during treatment, or within 30 days following the last final dose of treatment, whether or not they are related to the study, must be recorded.

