9.4 Deaths, Serious Adverse Events, and Other Significant Adverse Events

The number of deaths will be presented along with the corresponding reason for death.

On study serious adverse events will be classified by system organ class and preferred term. They will be presented overall by treatment group and by worst severity. Drug-related serious adverse events will also be tabulated.

On study adverse events leading to discontinuation will be classified by system organ class and preferred term. They will be presented overall by treatment group and by worst severity. Drug-related adverse events leading to discontinuation will also be tabulated.

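### SAP 9.3 admits adverse events to the by-arm summaries by start date alone, so an event already open at first dose that worsens on study drug can go uncounted

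*SAP*

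**What the plan says.** SAP 9.3 sets the entry rule for the adverse event tables: "On-study AEs are those with a start date on or after the first treatment dose date". The same sentence closes the window 30 days after the final application. Both limits are tests on the start date. The main table uses that set: "On-study adverse events will be summarized overall by treatment group and by worst severity".

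SAP 9.4 uses the same term twice more: "On study serious adverse events will be classified by system organ class and preferred term", and "On study adverse events leading to discontinuation will be classified by system organ class and preferred term".

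The listing is wider. "All adverse events will be presented in a listing which includes first treatment dose date, onset and resolution date/day", together with seriousness, severity, relationship, action taken and outcome. It is not limited to on-study events.

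On the protocol side, sections 12.2.2 and 12.4.1 collect adverse events from the signing of consent. Section 12.2.2 treats a condition present at screening as medical history, and adds that "if the condition worsens at any time during the study, it will be recorded and reported as an AE". Section 12.4.2.1 follows a recorded event until it resolves or another stopping point is reached. It does not say whether an increase in severity updates the existing record or opens a new one.

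Protocol Table 3 places SRP before randomization and before Day 1, with adverse events assessed at each of those visits. Its first footnote says "Product administration must occur within 3 days of the last SRP visit" and also allows the first application on the same day as the last SRP session.

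**The concern.** An event that is open at first dose and gets worse afterwards is normally counted as emerging on treatment, because the worsening happened under exposure. The SAP definition has no such branch. If the event stays on one record with its pre-dose onset, it fails the filter however severe it later becomes, and even if it becomes serious or ends treatment.

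The pre-dose period is one in which local events are plausible. Every subject has SRP under local anaesthesia, sometimes over several visits, and the product is then applied to the gingival margin in the same mouth. SAP 8.3.1 itself cites possible gingival swelling from SRP as a reason to leave the early visits out of the primary model. Local reactions that began after SRP and were aggravated by a topical product are events a reader of the safety tables would want counted.

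The frequency and pattern of adverse events is the safety endpoint, and safety is a secondary objective. SAP 9.1 makes the safety analysis descriptive with no testing, so the by-arm tables are the safety result. The disposition table in SAP 5.1 counts discontinuations for adverse events with no start-date filter, so it could also disagree with the filtered table in 9.4.

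**Working it through.** The plan gives no figure to reproduce here. The check applies the stated rule to dated examples and then measures the window in which it matters.

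**Rule.** Tabulate if: first dose date ≤ start date < last dose date + 30 days. Take Day 1 as first dose and Day 240 as the last scheduled dose, so the upper limit is 240 + 30 = Day 270.

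| Case | Start date on record | Tabulated? |
|---|---|---|
| (a) Event begins 3 days before Day 1, one record, worsens on study drug | 3 days before Day 1 | No |
| (b) Same event, worsening entered as a new record on Day 5 | Day 5 | Yes |
| (c) Event begins on the day of a combined SRP and first-dose visit | Day 1 | Yes |
| (d) Condition present at screening worsens on Day 20, recorded then | Day 20 | Yes |
| (e) Condition present at screening worsens before Day 1, recorded then | before Day 1 | No |

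Cases (a) and (b) are the same clinical course. Only the recording convention separates them, and neither document fixes it. The instruction in Protocol 12.4.2.1 to follow a recorded event to resolution sits more naturally with a single continuing record, which is case (a). The SAP listing shows onset, resolution and severity but no date of worsening, so case (a) could not be recovered by programming from the listed variables alone.

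Case (d) is the situation Protocol 12.2.2 addresses, and it passes the filter. Case (e) falls outside it, but correctly so unless the event worsens again after dosing, when it becomes case (a).

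**Window, from Protocol Table 3.**

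- Last SRP session to first dose: 0 to 3 days.
- Baseline to first dose: SRP within 10 days of baseline, plus 3 days, gives 10 + 3 = 13 days at most, before any unscheduled SRP visit.
- Screening to first dose: 30 + 10 + 3 = 43 days at most. Up to 30 of these precede the baseline visit, and so precede SRP.

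For events following SRP the relevant span is therefore up to 13 days, since SRP may begin on the day of the baseline visit and take more than one visit.

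**Which outputs are affected.** The overall on-study table (9.3), the serious event table (9.4) and the discontinuation table (9.4) carry the filter. The listing and the count of deaths do not. The sentences on drug-related events in 9.3 and 9.4 do not repeat the words on-study, so their scope is unclear.

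**The case against.** The best defence is that the loss is conditional. If sites enter the worsening as a new event dated when it occurs, the rule tabulates it. The eCRF completion instructions that would settle this are not among the documents. Where SRP and the first dose share a day, an event starting that day qualifies. Nothing disappears altogether: the listing holds every event with first dose date and onset, deaths are unfiltered, and serious events must be reported to the sponsor whatever their relationship to treatment. Safety is descriptive, so no test result changes. All of this stands, and it limits the point. It does not remove it, because a listing gives no rates by arm and the SAP should not rely on an unstated site convention.

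Three stronger readings are tempting and are not supported.

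- A reader might infer that Protocol 12.2.2 and SAP 9.3 contradict each other. They do not. The protocol clause concerns conditions present at screening. Their worsening is a new adverse event and, if dated at the worsening, passes the SAP rule. An event arising after SRP lies outside that clause.
- A reader might infer that such events vanish from every safety table. Exclusion depends on the onset date kept, and the drug-related tabulations do not restate the filter.
- A reader might infer a size, or a bias towards no difference between drug and placebo. The documents give no rate of events ongoing at first dose and no rate of worsening by arm. The phase 1 gingivitis study reported 125 events or oral findings in 54 subjects, all mild, with all related or possibly related events in two placebo subjects. That is a different population and does not supply either rate. If worsening were commoner on placebo, the filter would hide a benefit instead.

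**Conclusion.** The point holds as a gap in the definition. Followed literally, SAP 9.3 and 9.4 leave out of the on-study adverse event, serious event and discontinuation summaries any event that began before Day 1, was kept under its original onset date, and worsened, became serious or led to discontinuation after dosing. The conclusion rests on one assumption, that worsening is recorded on the existing record. The protocol text leans that way but does not state it.

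The window is real, since every subject has SRP before first dose, but it is short: 0 to 3 days after the last session and at most 13 days from baseline by the scheduled windows. The number of events affected and the direction of any bias cannot be derived from the documents. The change is worth making before database lock because it is cheap and the tables are the safety result. Nothing here bears on the efficacy analysis.

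**What to change.** 1. In SAP 9.3, define on-study adverse events as those that start, or that started earlier and increase in severity or become serious, on or after the first dose date and before the last dose date plus 30 days.
2. In SAP 9.4, apply that definition to serious events. In the discontinuation table, count any adverse event that led to discontinuation after the first dose, whatever its start date, so that the table can be reconciled with the disposition count in 5.1.
3. State whether the drug-related tabulations in 9.3 and 9.4 use the on-study set.
4. For adverse events ongoing at first dose, have the eCRF capture the date of worsening, or instruct sites to open a new record dated at the worsening. Without one of these the criterion in step 1 cannot be programmed. For records already entered, the events to query are those with onset before first dose that were not resolved by then.

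The cost is a sentence or two in each SAP section, a line in the eCRF instructions, slightly more programming, and slightly higher adverse event counts in all arms.

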**Table 5: Treatment Windows by Group (+/- Days)**

	Visit Day									
Groups 1, 3	≤12	22	30	60	90	120	150	180	210	240
	N/A	3	3	3	5	7	7	7	7	7
Group 2	≤ 90					120	150	180	210	240
	N/A					7	7	7	7	7

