### 12.4. Collection and Recording Adverse Events

#### 12.4.1. Period of Collection

All AEs and SAEs will be collected from the time the informed consent is signed until the end of the study. All AEs and SAEs that occur after any subject has signed consent, before treatment, during treatment, or within 30 days following the final dose of treatment, whether or not they are related to the study, must be recorded.

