2.4 Treatment Regimens

Group 1: ST266 dosed daily on Days 1-5, 8-12, 22, and 30 and then monthly for 7 months (Days 60, 90, 120, 150, 180, 210, and 240).

Group 2: ST266 dosed 2x/week (with at least one day between treatments) for the first 3 months and monthly for 5 months thereafter (Days 120, 150, 180, 210, and 240).

Group 3: Placebo dosed at the same frequency as Group 1.

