4. ANALYSIS POPULATIONS

Statistical analyses will be based on the analysis populations as defined below:

- Safety population: All randomized subjects who use at least one dose of study drug, regardless of whether or not they undergo any study assessments.
- Intention-to-Treat (ITT) population: All randomized subjects.
- Per Protocol (PP) population: All subjects who use at least one dose of study drug and do not have major protocol deviations as defined in § 5.2.

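### SAP 9.3 stops counting on-study AEs one day short of the protocol's 30-day limit, so at planned timing an event starting on the Day 270 end-of-study visit is missing from the on-study AE and SAE tables

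*SAP*

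**What the plan says.** SAP 9.3 counts an AE as on-study if it starts on or after the first dose date and "prior to the last treatment dose date + 30 Days". The AE summary in 9.3 is limited to on-study events. In 9.4 so are the SAE table and the table of AEs leading to discontinuation. The AE listing in 9.3 covers all AEs, and the count of deaths in 9.4 has no stated window.

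Protocol 12.4.1 gives two limits side by side. The first is "All AEs and SAEs will be collected from the time the informed consent is signed until the end of the study". The second requires recording of events "within 30 days following the final dose of treatment". Protocol 12.2.2 (AEs) and 12.2.3 (SAEs) repeat the 30-day limit and do not mention the end of the study.

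In SAP 2.4, Group 2 is dosed "monthly for 5 months thereafter (Days 120, 150, 180, 210, and 240"). Group 1 also ends on Day 240, and Group 3 follows the Group 1 schedule. Protocol Table 3 sets the final visit at "Visit 10/EOS Day 270 (±7 days"), with an oral exam, laboratory tests and AE assessment. Protocol Table 5 allows 7 days either side of the Day 240 dose. SAP 9.1 states: "Safety analyses will be presented descriptively on the safety population".

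**The concern.** The SAP limit is strict and the protocol limit is not, so the two differ by one day. At planned timing that day is the end-of-study visit, when AEs are actively sought. Day 270 is also one of only two post-screening laboratory time points, and Protocol 12.4.1.1 makes a clinically significant abnormal result an AE. The documents give no rule for dating the onset of a finding first seen at a visit. If it is dated to the visit, which is an assumption, the finding drops out of the AE tables.

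Safety is a secondary objective, and its endpoint is how often and in what pattern AEs and SAEs occur. The on-study tables are where that endpoint is reported. An SAE that starts on Day 270 would be recorded and listed but not counted in the SAE table.

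**Working it through.** **Inputs.** Last planned dose: Day 240 in all groups (SAP 2.4). End-of-study visit: Day 270 (Protocol Table 3). SAP rule: start day < last dose day + 30. Protocol rule: start day ≤ last dose day + 30, reading the protocol's 30 days as including the 30th. The plan states no figure to reproduce here.

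**Planned timing.**
- Limit: 240 + 30 = 270.
- SAP rule (start < 270): the last counted day is Day 269.
- Protocol rule (start ≤ 270): the last day is Day 270, since 270 − 240 = 30.
- Difference: 270 − 269 = 1 day, which is the end-of-study visit.
- All groups share the Day 240 last dose, so the difference is the same in every arm.

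**What an inclusive limit leaves open.** The dose and the final visit may each move by 7 days (Protocol Tables 5 and 3). Days left out up to the visit are max(0, visit − (dose + 30) + 1) under the strict limit and max(0, visit − (dose + 30)) under the inclusive one.

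| Last dose | Final visit | Strict limit | Inclusive limit |
|---|---|---|---|
| Day 240 | Day 270 | 270 − 270 + 1 = 1 | 0 |
| Day 240 | Day 277 | 277 − 270 + 1 = 8 | 7 |
| Day 233 | Day 277 | 277 − 263 + 1 = 15 | 14 |
| Day 247 | Day 270 | 0 | 0 |

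Wherever the strict limit leaves days out, the inclusive limit recovers exactly one. The remaining days are more than 30 days after the last dose. They fall inside the protocol's collection to the end of the study but outside its 30-day limit.

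**What is not lost.** Events that start before the limit are counted even if first reported at Day 270. All AEs are listed. Day 270 laboratory values and vital signs are tabulated by visit (SAP 9.5, 9.6.1). The table of AEs leading to discontinuation is hardly affected, because planned dosing is over by then.

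**The case against.** The strongest reply is that a tabulation window need not equal the collection period. The protocol also collects AEs from consent onward, and the SAP tables leave out pre-dose events without anyone calling that an error. A cut-off tied to exposure is a normal choice, and Protocol 12.2.2 and 12.2.3 support 30 days after the final dose. This stands. It means that ending the tables at 30 days is not itself a mistake. It does not defend the missing 30th day, which the same sections include.

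Four stronger readings are tempting, and the documents do not support them:

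- **That the rule excludes the final visit in most cases.** A reader could count date pairs within the windows: 15 dose days × 15 visit days = 225. The visit day is excluded in 15 × 16 / 2 = 120 pairs under the strict limit and 15 × 14 / 2 = 105 under the inclusive one. Only 120 − 105 = 15 pairs come from the boundary; the rest come from using a 30-day window at all. Pairs are also not patients, since the documents say nothing about how actual dates will be distributed.
- **That subjects who stop dosing early lose months of events.** Protocol 8.4 brings the final visit forward for those who leave the trial. Protocol 12.1.6 lets the Medical Monitor stop dosing but does not say whether the subject then stays to Day 270. Such subjects would remain in the safety population ("All randomized subjects who use at least one dose of study drug, regardless of whether or not they undergo any study assessments"), but their number is unknown, and their late events would be more than 30 days off treatment.
- **That the drug-related tables use a different window.** They carry no on-study qualifier, but each directly follows an on-study sentence and reads most naturally as a subset of that table. A clarifying word is enough.
- **That the arms are treated unequally.** The last planned dose is on the same day in every arm.

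**Conclusion.** The SAP rule is wrong as written at its boundary. It conflicts with the protocol's 30-day limit, and no other section of the SAP corrects it. At planned timing it removes one onset day, Day 270, from the on-study AE and SAE tables, equally in all arms. Safety is descriptive with no testing, and the events remain in the listing, so this is a minor completeness error and not a source of bias.

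The size rests on the last dose falling on Day 240 and the final visit on Day 270, on a literal reading of the SAP limit, and on the protocol's 30 days including the 30th. How many events will start on that day cannot be known from the documents. Events after day 30 but before the final visit are a secondary matter: leaving them out is defensible, but showing them serves the protocol's collection to the end of the study.

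**What to change.** - In SAP 9.3, change the upper limit to on or before the last treatment dose date plus 30 days.
- Also tabulate events that start after that limit and up to the end-of-study visit, flagged as more than 30 days after the last dose, so that the 30-day view and the whole-follow-up view are both available.
- State that the drug-related AE and SAE tables in 9.3 and 9.4 use the same window as the tables they follow.

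The cost is a sentence or two in the SAP, one date comparison and one flag in the program. SAP Section 1 places the SAP before database lock, so the change can be made in time. The downside is that a few off-treatment events are shown; the flag identifies them.
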